Date: July 1, 2013
Principal Investigator: [name]
Application Number: NA_00045673

Johns Hopkins Medicine - eForm A

1. Abstract

- a. Provide no more than a one page research abstract briefly stating the problem, the research hypothesis, and the importance of the research.

X-linked adrenoleukodystrophy (X-ALD), a progressive neurodegenerative disease, is caused by a defect in the ABCD1 gene. The disease has multiple phenotypes, but the most common adult form is adrenomyeloneuropathy (AMN), which presents as a slowly progressing spastic paraparesis with sensory and autonomic dysfunction. In a previous study we linked corticospinal tract (CST) and Dorsal Column (DC) abnormalities to lower extremity sensory loss and weakness in men with AMN; however, there have been no studies evaluating these relationships in woman heterozygote carriers (i.e., women with AMN). It is unknown, in women with AMN, how the pattern of damage in the brain and spinal cord relates to disability and if these patterns predict responsiveness to treatment. While conventional magnetic resonance imaging (MRI) techniques have been used to evaluate progression of X-ALD disease burden, attempts at correlating clinical disability with axonal injury have had limited success due to clinical rating scales that do not adequately measure all aspects of the disease, coupled with an inability for routine imaging techniques to quantify relevant fiber tracts in the brain and spinal cord. We propose to comprehensively evaluate the CST and DC across the brain and cervical spinal cord with the purpose of understanding mechanisms of disability in women with AMN. We hypothesize that: 1) tract-specific magnetization transfer imaging (MTI) and diffusion tensor imaging (DTI) will predict specific sensory and motor impairments (i.e., sensory loss and weakness) and disability; and 2) tract-specific MTI and DTI will predict who is likely to respond best to progressive resistive training (PRT). For this project we are using a rigorous biologic approach that combines clinical evaluation, neuroimaging, and measures of impairment and disability to provide a more precise prognosis in terms of physical disability and to predict who is likely to respond to a physical intervention. We predict that many of the women will improve their strength and function following the PRT program. Specifically, we predict that axonal loss will be associated with irreversible disability. By contrast, demyelination may have potentially reversible injuries that would benefit from PRT in improving disability. The linking of this information will not only be important for better defining disability in women heterozygote carriers of AMN but it will also help to guide physicians and rehabilitation therapists in predicting who is likely to respond to rehabilitative interventions, as well as for optimizing outcomes for future neuroprotective pharmacological interventions.

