Conventional magnetic resonance imaging techniques along with the Loes scale (i.e., categorical rating scale) have been used to evaluate progression of X-ALD disease burden in children with moderate success. Pathologic studies show that dying back of axonal loss is a primary pathogenic mechanism of AMN and much of the permanent disability results from axonal damage. However, attempts at correlating clinical disability with axonal injury have had limited success due to clinical rating scales that do not adequately measure all aspects of the disease, coupled with an inability for routine imaging techniques to depict specific clinically involved fiber tracts in the brain and spinal cord. Our preliminary data show that we can distinguish female carriers from control subjects using novel techniques such as magnetization transfer (MT) imaging. In addition, we have previously shown that damage measured using tract specific MRI, specifically magnetization transfer and diffusion tensor imaging (DTI) correlates with physical impairments in individuals with the degenerative disease of multiple sclerosis.

In conjunction with advanced DTI and MT metrics developed at the Kirby Imaging Center of the Kennedy Krieger Institute, we plan to capitalize on the tools within our motion laboratory, having thorough experience with them in assessing spasticity, ataxia, sensation, and muscle strength in individuals with AMN and in individuals with multiple sclerosis. We predict that MT imaging and DTI, which measure the integrity of white matter and fiber tracts in the brain and spinal cord, will aid in understanding the extent to which axonal/myelin anatomy are associated with sensory and motor impairments as well as locomotor patterns with the goal of understanding how to treat physical disability more effectively.

4. Study Procedures

- a. Study design, including the sequence and timing of study procedures (distinguish research procedures from those that are part of routine care).

Date: July 1, 2013
Principal Investigator: [name]
Application Number: NA_00045673

We will test female heterozygote carriers of X-ALD and healthy age- and gender-matched controls.

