Healthy controls have the same exclusion criteria as women with AMN with 2 exceptions, (1) they can be age 21-70 years, and (2) they will not be carriers for X-ALD. They must have normal neurological function.

6. Drugs/ Substances/ Devices

- a. The rationale for choosing the drug and dose or for choosing the device to be used.

N/A

- b. Justification and safety information if FDA approved drugs will be administered for non-FDA approved indications or if doses or routes of administration or participant populations are changed.

N/A

- c. Justification and safety information if non-FDA approved drugs without an IND will be administered.

N/A

Study Statistics

- a. Primary outcome variable.

Primary outcome variables for sensorimotor impairments include: vibration sensation, strength (average values from the hip and ankle muscles, both flexion and extension, will be used), and spasticity from the ankle flexor/extensor muscles bilaterally.

The primary variables of interest for white matter integrity in this analysis will be fractional anisotropy (FA) and magnetization transfer ratio (MTR).

Other primary outcome variables include correlations to determine relationships between sensorimotor impairments and between white matter integrity variables in the tracts of interest. Multiple regression analysis we will also be used determine to what extent sensorimotor impairments are related to white matter integrity variables.

The primary outcome variable for the exercise intervention we will calculate a functional composite score (FS) for each person that will incorporate 4 tests that functionally challenge the lower extremity: 1) sit to stand, 2) Up and Go test, 3) 25-foot timed walk, and 4) 6-minute walk test.

- b. Secondary outcome variables.

To determine response to three months of the exercise intervention:

1. We will calculate pre- to post- trial differences between groups using an unpaired t test. Changes between pre- and post-trial within groups will also be compared with paired t tests.

Date: July 1, 2013
Principal Investigator: [name]
Application Number: NA_00045673

2. To determine change in hip flexion, FS from post- to follow up session within groups will be compared with paired t tests. [(Exercise_{followup}-Exercise_{post}) vs (Exercise_{post}-Exercise_{pre})], will be evaluated.

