 3. To evaluate possible time and group interactions during the intervention within groups we will use multivariate ANOVA's. Significant interactions will be evaluated with a mixed effects linear regression.
 4. To determine change in EDSS scores over each session we will use with Wilcoxon signed rank test.
 5. To determine whether specific changes in the primary outcome measures are predicted by the changes in tract specific demyelination and axonal loss (i.e., MTR and FA) we will determine how much each impairment changed from the pre- to post- session.
 6. We will conduct separate correlations to determine the relationship between the primary outcomes, and extent of demyelination and axonal loss pre- and post-intervention.
 7. Multiple regression analyses will also be used to determine which pattern of white matter damage (i.e., demyelination, axonal loss) best predicts hip flexion and FS.
- c. Statistical plan including sample size justification and interim data analysis.

Preliminary studies of heterozygote data from our laboratory suggest that a minimum of 12 subjects are needed to obtain adequate statistical power. Hip flexion strength data from female carriers are: 11.2 ± 4.6 kg. Using these values, differences between groups on the order of one SD will be statistically significant with a power of 0.8 given a sample size of 12 subjects. To account for attrition, we have added 25% to this total. Therefore, our initial plan is to have 15 female carriers for this project and 15 healthy controls. All power calculations assume two-tailed tests with $\alpha = 0.05$. Analysis will be done using Statistica software (StatSoft Inc., Tulsa OK) or Stata (StataCorp).

- d. Early stopping rules.

None.

7. Risks

- a. Medical risks, listing all procedures, their major and minor risks and expected frequency.

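### The stated power of 0.8 for a one-SD difference between groups is wrong: it is 65% with 12 completers per group and 75% with 15

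*Combined protocol and SAP*

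**What the plan says.** The sample-size paragraph (Study Statistics, c) has one numerical input: "Hip flexion strength data from female carriers are: 11.2 ± 4.6 kg". From it the plan concludes that "differences between groups on the order of one SD will be statistically significant with a power of 0.8 given a sample size of 12 subjects". All power calculations are declared two-tailed with alpha 0.05. The plan then adds 25% for attrition, so that "our initial plan is to have 15 female carriers for this project and 15 healthy controls".

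The intervention analyses are listed under Study Statistics, b. Item 1 reads "We will calculate pre- to post- trial differences between groups using an unpaired t test" and continues "Changes between pre- and post-trial within groups will also be compared with paired t tests". The groups are defined in section 4a: "We will test female heterozygote carriers of X-ALD and healthy age- and gender-matched controls". Sections 4c (blinding) and 7b (risk minimisation) both say that every subject exercises, so the controls train too. For the intervention outcome, Study Statistics, a, says "The primary outcome variable for the exercise intervention we will calculate a functional composite score (FS) for each person". The Abstract adds an expectation about the carriers: "We predict that many of the women will improve their strength and function following the PRT program".

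**The concern.** This is the only power statement in the plan, and it is made for a comparison between groups. One SD with 12 per group is a small two-sample design, and 80% looked too high for it. If the true figure is lower, the investigators and the ethics board are relying on a wrong chance of success.

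The paragraph also does not say what is compared. It may mean hip flexion level in carriers against controls, or the training gain of item 1. The 4.6 kg is a spread of strength values across women, not a spread of pre-post changes, so the two readings need different inputs. No SD, effect size or power is given for the functional composite score.

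**Working it through.** **Inputs.** From Study Statistics, c: two-sided alpha 0.05; effect d = 1 SD; stated power 0.8; 12 subjects; SD 4.6 kg; 25% added; 15 carriers and 15 controls. Assumed: equal SD in the two groups (no control SD is given) and, for gain in kg, a pre-post correlation r (none is given).

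**Step 1: what 12 means.** 12 × 1.25 = 15, and 15 are planned in each group, so 12 is the number of completers per group.

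**Step 2: trying to reproduce 0.8.** For an unpaired t test with n per group, df = 2n − 2 and the noncentrality is d√(n/2). At n = 12 and d = 1 this is √6 = 2.449 on 22 df, against a critical value of 2.074.

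| n per group | noncentrality | power, d = 1 |
|---|---|---|
| 6 (if 12 were the total) | 1.732 | 34.7% |
| 12 | 2.449 | 64.9% |
| 15 | 2.739 | 75.3% |
| 16 | 2.828 | 78.1% |
| 17 | 2.915 | 80.7% |

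The normal approximation gives 68.8% at 12 and 78.2% at 15. The nearest match found at 12 per group is a one-sided normal approximation, 78.9%, which contradicts the declared two-tailed tests. A paired test with n = 12 (noncentrality √12 = 3.464 on 11 df) gives 88.3%, which is not 0.8 either. The stated figure therefore does not reproduce under the stated conditions.

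**Step 3: difference detectable with 80% power.** Unpaired: 1.197 SD at 12 per group and 1.060 SD at 15. With 4.6 kg as the SD in both groups, 1.197 × 4.6 = 5.5 kg and 1.060 × 4.6 = 4.9 kg. The 4.6 kg the plan counts on is 4.6/11.2 = 41% of the carrier mean.

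**Step 4: does the reading matter?**

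- *Level of hip flexion.* With the same SD in controls, Step 2 applies directly: 65% and 75%.
- *Gain, with one SD meaning one SD of change.* Step 2 again applies directly.
- *Gain, with a difference of 4.6 kg.* The SD of change is 4.6√(2(1 − r)), so d = 1/√(2(1 − r)).

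| r (assumed) | d | 12 per group | 15 per group |
|---|---|---|---|
| 0 | 0.71 | 38% | 46% |
| 0.3 | 0.85 | 51% | 61% |
| 0.5 | 1.00 | 65% | 75% |
| 0.7 | 1.29 | 86% | 93% |

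With 12 per group, 80% is reached at r of about 0.65.

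**Step 5: the paired test, for comparison.** With 12 carriers, 80% power is reached at a mean change of 0.889 SD of change; with 15, at 0.778. At one SD of change, power is 88% (12) or 95% (15). If the change is instead 4.6 kg, power with 12 carriers is 61% at r = 0, 76% at r = 0.3 and 88% at r = 0.5.

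**The case against.** **The paragraph may not be about item 1.** It neither cites item 1 nor mentions change or gain, and its only input is a cross-sectional strength value. A reader might infer that the study was sized on the difference in training gain between carriers and controls. The documents do not say so, and a difference in strength level is at least as natural a reading. This stands, but it does not rescue the 0.8, because the two-sample shortfall is the same for level under equal SDs.

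**The paired test might be what was meant.** A reader might infer that 0.8 with 12 subjects holds for the paired within-carrier test, and that the sample size should be tied to it. The documents do not support this. The sentence names groups, the paired figure at one SD is 88%, and that figure requires one SD of change, for which no value is given. The paired test is listed under secondary outcomes, and neither primary objective in section 2 is mean change in carriers; the second is about imaging predicting response. Moving the 12 onto that test would fit the justification to the number already chosen. It would also rest on an uncontrolled pre-post comparison with unblinded testers (section 4c).

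**No analysis is missing.** Correct. Item 1 plans both the unpaired and the paired test, and item 3 adds time-by-group analyses. Relabelling item 1 would change no result.

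**The kg figures are uncertain.** Also correct. The hip flexion entry range in section 5, 6.6 to 15.8 kg, is exactly 11.2 ± 4.6, so women entering by that route would vary less than 4.6 kg suggests. The alternative hip extension route leaves the enrolled spread unknown. This affects the conversion to kg, not the power at one SD.

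**Conclusion.** The power statement is wrong as written. For a one-SD difference between two groups, two-sided alpha 0.05, power is 65% with 12 completers per group and 75% if nobody is lost. The chance of missing such a difference is thus about 35% or 25%, not 20%. Reaching 80% needs 17 completers per group, or a true difference of 1.20 SD (12 per group) or 1.06 SD (15).

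This rests on 12 meaning per group (if it were the total, power would be 35%), on equal SDs, and on one SD being that of the variable compared. For a 4.6 kg difference in gain no single figure can be given, and above r of about 0.65 the stated 0.8 would be met.

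The documents do not show that the paired within-carrier comparison is underpowered; its power is simply not stated. One caution on interpretation follows from the design. Since controls also train, item 1's unpaired test estimates carrier gain minus control gain, so a null result there is compatible with real improvement in both groups.

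This should be corrected, but it does not call for a redesign.

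**What to change.** Keep the planned 15 and 15, and replace the power sentence in Study Statistics, c. Suggested text: *With 12 completers per group, power is 65% for a between-group difference of one SD (75% with 15 per group), two-sided alpha 0.05; 80% power is reached for a difference of 1.20 SD (1.06 SD with 15).*

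In the same paragraph:

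- Say whether the comparison is of level or of pre-post gain, and on which outcome. If gain in kg is meant, state the SD of change or the assumed pre-post correlation.
- Optionally add, as a separate conditional statement and not as the basis of the 0.8, that 12 carriers give the paired test 80% power for a mean change of 0.89 SD of change.
- Add to item 1 that, because controls train as well, a null unpaired result is not evidence that carriers did not change.

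The cost is a few sentences, with no extra participants, visits or analyses. The documents contain no SD of change, so any figure given would have to be labelled as an assumption. The downside is that the stated between-group power becomes less favourable.

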exercise log to complete. If participants miss a training session a substitute session will be arranged on an alternate day.

Subjects will also go through Magnetic Resonance Imaging (MRI) in the F.M. Kirby Center at the Kennedy Krieger Institute. Prior to the start of imaging each subject will be asked to complete a standard questionnaire, this will ensure that the subject is able to safely enter the area where the MRI scan will take place. Subjects will undergo imaging without contrast and without sedation. For this study we will use a 3T Philips GyroscanNT (Best, The Netherlands) system to obtain high-resolution anatomical brain and spinal cord images. In the brain and spinal cord, diffusion tensor imaging (DTI) will be performed as well as magnetization transfer (MT). Conventional brain and spinal cord (STIR, T1w, T2w) sagittal and axial images may also be acquired. The total scanning time will be approximately 1 hour.

Analysis of the DTI images will be done using custom written software (DTI-Studio) or custom Matlab programs to calculate the diffusion tensor variables at each pixel and create 2D color maps of white matter pathways. Analysis of MT will be calculated on a voxel by voxel basis by the following equation: $MTR=1-S/S_0$ where S and S_0 are the images acquired with and without MT prepulse, respectively.

The measurements made with these activities are for research purposes only and at this time will have limited direct clinical utility, but results can be given to the subject or their physician. If the subject would like us to provide results they will be instructed to let us know during their testing, or they can ask us over the telephone after their visit and we will send the information to them.

Incidental findings on MRI will be provided to the patient by [name] by either phone or if necessary in a clinical visit. The individual will be assisted in obtaining follow up care.

b. Study duration and number of study visits required of research participants.

Each testing session will require about 1.5 hours of time, with one session requiring 3.5 hours of time due to a 1-hour MRI scan and an hour for exercise instruction. All subjects will be tested a total of three times: baseline, 12 weeks, and 18 weeks after baseline. Based on the results of this study we will ask subjects if they would be willing to come back for future visits, this is not mandatory for participation.

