c. Blinding, including justification for blinding or not blinding the trial, if applicable.

All subjects in the study will take part in the exercise intervention. We are unable to blind the subjects or testers to the intervention which has been discussed in other similar studies as a limitation. However, we have specified guidelines that the PT will follow for progression of the exercise program to alleviate bias as much as possible.

d. Justification of why participants will not receive routine care or will have current therapy stopped.

N/A

Date: July 1, 2013
Principal Investigator: [name]
Application Number: NA_00045673

e. Justification for inclusion of a placebo or non-treatment group.

N/A

f. Definition of treatment failure or participant removal criteria.

Patients selected for the study will be removed if they: 1) inform us that they become pregnant during the study, 2) are unable to follow the requirements of the study, or 3) request to be removed.

We are not aware of a particular pregnancy risk, but the inclusion of a subset who are pregnant would be difficult to interpret compared to non-pregnant participants.

g. Description of what happens to participants receiving therapy when study ends or if a participant's participation in the study ends prematurely.

The subject's medical care will continue unaltered when the study ends or if a subject is removed from the study.

5. Inclusion/Exclusion Criteria

Inclusion criteria for women with X-ALD

- confirmed diagnosis, X-ALD heterozygote carrier
- no medical contraindication to participating in a strength training program
- able to follow complex directions as determined by a score of ≤ 1 on a subset of questions taken from the NIH Stroke scale (Brott et al. 1989)
- hip flexion strength: 6.6-15.8kg or hip extension strength: ≤ 18.3 kg
- normal passive range of motion at hips/knees/ankles
- scale of 1-6 on the EDSS
- able to walk ≥ 50 m
- age 21-65

Exclusion criteria

- Evidence of other neurological deficit that could interfere, such as previous stroke or muscle disease
- congestive heart failure
- cancer
- orthopedic conditions
- severe pain that precludes study participation
- seizures
- pregnancy
- other medical condition that precludes participation in an exercise program, e.g., unstable angina, uncontrolled diabetes, uncontrolled hypertension

Date: July 1, 2013
Principal Investigator: [name]
Application Number: NA_00045673

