treatment. Our comprehensive methodology and careful quantification of sensory and motor impairments and walking may be a more sensitive way to quantify subtle changes in disability, and may be more closely related to the function of the corticospinal tract. Our results, therefore, have the potential to support new clinical markers that more closely follow changes in physical function in AMN. We are also directly testing a treatment intervention that will provide scientific rationale for predicting the best responders to a progressive resistance training program. We will evaluate not only the improvement in physical function but also the extent that myelin and axon structure and integrity can predict who best responds to the intervention. Overall, the linking of clinical impairments and disabilities with anatomic MRI measures will not only be important for better defining disability in female carriers but it will also help to guide physicians and rehabilitation therapists in predicting who is likely to respond to rehabilitative interventions, as well as for optimizing the effects of future neuroprotective pharmacological interventions.

9. Payment and Remuneration

- a. Detail compensation for participants including possible total compensation, proposed bonus, and any proposed reductions or penalties for not completing the protocol.

All subjects will be compensated \$25 for participating in the laboratory sessions. Subjects will be paid in cash upon completion of the study. If subjects leave the study before it is completed, they will not receive payment.

10. Costs

- a. Detail costs of study procedure(s) or drug (s) or substance(s) to participants and identify who will pay for them.

The subjects will not be charged for any of the procedures in the study. They will only be responsible for the cost of any travel to and from the Institute as well as any meals they eat while participating. The costs of parking at the Institute's garage will be covered. All subjects will be provided \$150 for the costs of their participation in the exercise program. MRI scan fees for women carriers will be covered by a research grant from the European Leukodystrophy Association. Requests for further financial support are underway through the NBRU, and NIH mechanisms. Funding for up to four individuals is also available to help offset the financial burdens of travel costs.

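### Item 3's mixed-model estimate appears only after a significant interaction, and the plan does not say whether removed women are still tested

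*Combined protocol and SAP*

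**What the plan says.** **Item 3** (Study Statistics, b. Secondary outcome variables). For time-by-group interactions, "we will use multivariate ANOVA's. Significant interactions will be evaluated with a mixed effects linear regression". No visits are listed. The sentence refers to the period of the intervention and adds a within-groups qualifier, which sits oddly with a test of a group interaction. Training lasts 12 weeks, and all subjects are tested at baseline, week 12 and week 18 (4. Study Procedures, a).

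**The neighbouring items.** Item 1: "We will calculate pre- to post- trial differences between groups using an unpaired t test". This compares the groups but ends at post. Item 2: "FS from post- to follow up session within groups will be compared with paired t tests". This reaches follow-up but does not compare the groups. Item 4 is a signed-rank test of EDSS change, also within person. Item 7 uses regression to predict hip flexion and the functional score (FS) from the pattern of white matter damage, which serves objective 2.

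**Removal.** In section 4f the second criterion reads "2) are unable to follow the requirements of the study". Section 4g, on early exit, says only: "The subject's medical care will continue unaltered when the study ends or if a subject is removed from the study". Section 9 adds: "If subjects leave the study before it is completed, they will not receive payment". On costs to subjects, section 10 says "They will only be responsible for the cost of any travel to and from the Institute", plus meals.

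**Safeguards against loss.** Section 4a says "If participants miss a training session a substitute session will be arranged on an alternate day", and staff contact the women by phone or email. Section 7b has a therapist progress the exercise to each woman's capability. Study Statistics c adds 25% to 12 subjects for attrition, giving 15 carriers and 15 controls. No method for missing outcomes is stated.

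**The concern.** An estimate that is produced only when a test of the same data is significant is a selected estimate. When there is a real difference, the trials that pass are on average those in which chance added to it. The reader of the report would see the inflated figures and no estimate or interval from the rest.

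At stake is whether carriers keep any gain relative to controls six weeks after training ends. Items 1, 2 and 4 do not address this, so it falls to item 3 if it is addressed at all.

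The removal rule raises a different question. Objective 2 asks who responds best, so it needs post-training outcomes from poor responders as well as good ones. If women who cannot keep up are removed and not tested again, and if they tend to respond poorly, the carriers' mean change and the relation between baseline MTR or FA and response may both be distorted.

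**Working it through.** **Inputs from the plan.** 15 per group, 12 after attrition; two-sided alpha 0.05; SD 4.6 kg for hip flexion; planned difference 1 SD (Study Statistics c). **Assumed, because the plan gives none:** correlation rho between visits (0.5, 0.7 or 0.8, equal for all pairs), normal data, and the dropout mechanisms in step 4.

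**1. The plan's own figure.** The plan states power 0.8 for 1 SD with 12 subjects. A two-sided, two-sample t test with 12 per group has power 0.65; 0.8 needs 17 per group. The stated figure is not reproduced on that reading. That is a separate matter; only the sample sizes and the SD are used below.

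**2. Pre/post reading.** With two visits and one outcome the interaction test is the unpaired t test on change, as in item 1. A between-woman difference d becomes d / sqrt(2(1 - rho)) in SDs of change: for d = 1, this is 1.00, 1.29 and 1.58 at rho 0.5, 0.7 and 0.8. Simulation (400,000 replicates) for 15 and 12 per group:

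- True 1.0 SD of change: 75% and 65% of trials pass; the mean passing estimate is 1.148 and 1.223, so 15% and 22% too high. Of the passing estimates, 34% and 24% are still below the truth, so the excess is an average.
- True 0.5 SD of change: 26% and 22% pass; 0.935/0.5 and 1.022/0.5 give 87% and 104% too high.

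Item 1 reports this same contrast without any gate.

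**3. Three-visit reading.** The gate is Hotelling's T-squared on the week-12 and week-18 changes, with the effect maintained to week 18 (60,000 replicates). Excess = mean week-18 estimate among passing trials / true value - 1. Pairs are for 15 and 12 per group.

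| True difference | rho | Trials passing | Mean week-18 estimate | Excess |
|---|---|---|---|---|
| 1 SD | 0.5 | 77%, 65% | 1.112, 1.177 | 11%, 18% |
| 1 SD | 0.7 | 94%, 87% | 1.029, 1.059 | 3%, 6% |
| 1 SD | 0.8 | 99%, 97% | 1.004, 1.015 | 0%, 2% |
| 0.5 SD | 0.5 | 25%, 20% | 0.849, 0.907 | 70%, 81% |
| 0.5 SD | 0.7 | 39%, 31% | 0.715, 0.767 | 43%, 53% |
| 0.5 SD | 0.8 | 55%, 45% | 0.628, 0.674 | 26%, 35% |

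In hip flexion terms, half an SD is 2.3 kg; at rho 0.5 and 12 per group the mean reported value would be 0.907 x 4.6 = 4.2 kg. If the difference is 1 SD at week 12 and fades to 0.5 SD at week 18, the excess at rho 0.5 is smaller: 0.594/0.5 and 0.637/0.5 give 19% and 27%.

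**4. Removal, illustrated.** Of 15 carriers, 3 have no post-training outcome (200,000 replicates). They are lost at random, by a score correlated 0.5 with gain (moderate), or as the 3 poorest (worst case). The mean gain of the remaining 12 is too high by 0, 0.16 and 0.33 SD of gain. As a check, the worst case means that the 3 lost women average 12 x 0.328 / 3 = 1.31 SD below the mean, and the moderate case is 0.5 x 0.328 = 0.164.

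Power to detect a baseline predictor of gain:

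| True r | None lost | Random | Moderate | Worst |
|---|---|---|---|---|
| 0.3 | 19% | 16% | 15% | 12% |
| 0.5 | 50% | 40% | 37% | 27% |
| 0.7 | 88% | 78% | 74% | 60% |

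The step from none to random is ordinary attrition. At r = 0.5, selection takes a further 3 points (moderate) to 13 points (worst).

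**The case against.** **The visits.** Item 3 speaks of the intervention period, which is 12 weeks, and the list is introduced as response to three months of exercise. Both favour pre/post. This is not conclusive, but it is the likelier reading, and on it the gate costs little. This stands.

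**The gate does not block the comparison.** A reader might infer that no unconditional analysis compares carriers with controls through week 18. The documents do not support that: the MANOVA is itself an unconditional time-by-group test and can include week 18 as far as the mixed model can. What depends on significance is the model estimate.

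**Missing visits.** A reader might infer that the mixed-model estimate would rest only on women with complete visits. It would not, since a mixed model uses every available visit. Complete-visit loss affects the MANOVA.

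**Assumed inputs.** Correlations, half-SD effects and dropout mechanisms are not in the plan. At the planned 1 SD and a correlation of 0.8, the excess is 2% or less. The MANOVA may also be meant to test several outcomes jointly, in which case the gate gives some control of multiplicity; that case was not simulated.

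**Removal.** A reader might infer that removed women are barred from testing. The plan is silent on this; it sets no ban, and it gives three tests for all subjects. The criterion is inability to follow requirements, not poor response, and the safeguards make removal less likely. All of this stands, but neither the safeguards nor the general visit schedule says what happens once a woman has been removed from the study.

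**Conclusion.** The concern holds in a limited form. Item 3 is the only planned analysis that could compare the groups through week 18, and its estimate is conditional on significance. If week 18 is meant and the effect is maintained, the mean reported estimate is about 0-18% too high for a true 1 SD and 26-81% for half an SD, given correlations of 0.5 to 0.8 and 12 to 15 per group. If pre/post is meant, little is lost.

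This should not be read as bias in a treatment effect. Both groups train, and the contrast is secondary and separate from objective 2.

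On removal, the finding is an omission: the plan does not say whether removed women are still tested or how their data are analysed. The documents give no dropout mechanism, so the 0 to 0.33 SD is an illustration, and the bias is zero if removal is unrelated to response. Both parts are worth correcting because the corrections cost little. Confidence is medium.

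**What to change.** **Item 3.** Name baseline, week 12 and week 18, and delete the within-groups qualifier. Fit the mixed-effects linear model (visit, group, visit-by-group, random participant effect, small-sample degrees of freedom) to all available visits whatever the MANOVA result, and report the estimate with its interval. Keep any MANOVA as a joint test, not as a condition for reporting. Cost: wording only, since the model is already named and the visits are already scheduled.

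**Removal.** State that a woman who stops training or cannot keep up with it is, with her consent, still invited to the scheduled week-12 and week-18 tests and kept in the analyses, with completers as a sensitivity analysis. State that attending those tests counts as completion for payment. Decisions on stopping exercise are unchanged.

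Cost: changed removal and payment wording and a few test visits. With about 3 women per group and at most 2 visits each, that is at most 2 x 3 x 2 = 12 visits and 6 x $25 = $150, plus the women's own travel, for which section 10 offers help to up to four people.

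**Limits.** This does not help a woman who cannot attend testing. Nor does it supply the post-training MTR and FA that items 5 and 6 call for, because section 4a schedules MRI at baseline only.
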